8.5.1.1 Multiplicity

All treatment groups will be assessed by pairwise comparisons. No adjustment will be made for multiple comparisons except for primary analysis.

8.5.1.2 Treatment by center interaction analysis (multi-center study)

No analysis will be made to assess the treatment-by-center interaction.

8.5.2 Analysis of primary efficacy endpoint

The primary efficacy endpoint for this study is the change in baseline in Tr. vBMD (radius) on HRpQCT and change from baseline in bone strength on FEA at 12 months. The primary endpoint and dose response analysis for the primary endpoint will be performed on the FAS population and repeated on the mFAS, Non-restricted FAS and the PP populations

8.5.2.1 Primary analysis

The HRpQCT results for the Trabecular vBMD (radius) will be log transformed and an ANCOVA model will be used to calculate the LSMMeans for the change from baseline as described in Section 8.5.1. The change from baseline LSMMeans for each treatment group will be tested against the null hypothesis of 0 using a t-test, in an a priori hierarchical approach, starting with the highest dose.

The LSMMeans and standard errors will be displayed at each visit as well as the corresponding P-value from each t-test.

Differences between LSMMeans, their confidence intervals and P-values will also be displayed but will be analysed in an exploratory fashion only. The type I error rate will be 5% two-sided. P-values above 5% but below 10% (two-sided) will be considered as indicative for a trend.

LSMeans and LSMeans differences between treatment groups will be back-transformed to their original scale for descriptive purposes. After subtracting the geometric mean of the log baseline values, the back transformed LSMMeans will correspond to the percentage change from baseline, while the back-transformed LSMMeans differences will correspond to the ratio of percentage changes from baseline.

Line graphs of the LSmean HRpQCT results (+/- SE) and change from baseline in HRpQCT results (+/- SE) will be presented.

A descriptive summary will also be presented for the non-log transformed HRpQCT results for the Trabecular vBMD (radius) values, change from baseline and percentage change from baseline in HRpQCT by treatment group and OI type.

For supportive evidence, the above analysis will be repeated on the mFAS, Non-restricted FAS in both versions and the PP population for HRpQCT results for the Trabecular vBMD (radius) and repeated for the bone strength on FEA for the FAS, Non-restricted FAS and PP population.

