11.3.1. Efficacy Analyses

Analyses for the primary efficacy endpoints and selected secondary endpoints will be analysed on the FAS, mFAS, the Non-restricted FAS and the PP samples, while analyses for the remaining secondary efficacy endpoints will be analysed on the FAS sample only. The mFAS will be used for analysis of HRpQCT endpoints only. General methods as described above will be applied to the efficacy endpoints; specific analyses are described below.

Endpoint	Statistical Analysis Methods
Primary	
The HRpQCT results for the Trabecular vBMD (radius) will be log transformed and an ANCOVA model will be used to calculate Least Square Means (LSMeans) for the change from baseline, using baseline values as a covariate and treatment group and stratum as a factor. LSMeans for each treatment group will be calculated and tested against the null hypothesis of 0 in an a priori hierarchical approach, starting with the highest dose. Differences between LSMeans will also be displayed but will be analysed in an exploratory fashion only. The type I error rate will be 5% two-sided. P-values above 5% but below 10% (two-sided) will be considered as indicative for a trend.
 
For supportive evidence, this analysis will be repeated on the mFAS, Non-restricted FAS in both versions and the PP population. Further,

Endpoint	Statistical Analysis Methods
	
the following analyses will be performed, again on the FAS, mFAS, the Non-restricted FAS in both versions and the PP population:
 
The LSMeans will further be analysed using the MCPMod methodology, using the following candidate models:
 
 • EMax (ED₅₀ of 1.5 mg) • Exponential ($\delta = 2$) • Sigmoid EMax model with parameters ED₅₀ = 10 mg and h = 2.4 
Parameter estimates and predicted values for each dose will be calculated for all models.
 
These analyses will be done primarily on the trabecular vBMD (radius). It will be repeated for the bone strength on FEA for supportive evidence.
 
LSMeans and LSMeans differences between treatment groups will be back-transformed to their original scale for descriptive purposes. After subtracting the geometric mean of the log baseline values, the back-transformed LSMeans will correspond to the percentage change from baseline, while the back-transformed LSMeans differences will correspond to the ratio of percentage changes from baseline.

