5 SAMPLE SIZE AND POWER

The number of participants is based on power considerations for the trabecular vBMD (radius) derived from HRpQCT at Month 12. The primary analysis method for this endpoint will be on the change from baseline within each treatment group, so the primary hypothesis to be tested is

$$H_0: \mu_T \leq 0 \text{ vs. } H_1: \mu_T > 0$$

where μ_T denotes the change from baseline for each dose of Setrusumab. Under the assumptions of a maximum change from baseline of [REDACTED], a standard deviation at both timepoints of [REDACTED] and a correlation between both measurements of [REDACTED] a sample size of 25 patients per group yields approximately 80% power for a one-sided test with significance level 0.025, if the data are analysed on the log scale using a t-test.

For a change from baseline of [REDACTED], with standard deviation as above the one-sided test would have a probability of 80% to yield a p-value below 5%, being considered indicative of a trend.

Following a review of the trabecular vBMD (radius) derived from HRpQCT at Month 6 of those patients within the 20mg/kg Setrusumab open label treatment group, a change from baseline standard deviation of [REDACTED] was observed. This yields to a correlation between baseline and month 6 visits of [REDACTED] (much higher than the [REDACTED] that was originally assumed). If such a correlation is observed at month 12, given 25 subjects per arm, the one-sided test would have a probability of 80% to yield a p-value below 5% for a change in baseline of [REDACTED].

As a secondary analysis, the MCPMod approach will be applied to the data in order to assess a non-flat dose-response curve and to obtain information about the underlying dose-response curve. Due to the missing placebo group, the power of this approach depends heavily on the underlying dose-response curve.

The following candidate models will be used:

- EMax (ED50 of 1.5 mg)
- Exponential ($\delta = 2$)

Under the assumptions of each of the two candidate models being the true dose-response curve, and in addition an Sigmoid EMax model with parameters ED50 = 10 mg and $h = 2.4$, a contrast test at a one-sided significance level of 2.5% has the following power for each of the three models:

Model	EMax	Exponential	Sigmoid EMax
Power	13.7%	73.2%	60.7%

The total sample size required is therefore determined as 100:

- 25 participants on open-label setrusumab (20 mg/kg)

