8.5.1 Analysis methods

For all continuous outcomes, where appropriate, an ANCOVA model analysis will be performed. Analyses will include the fixed, categorical effects of treatment and randomisation stratum as well as the associated baseline value as a covariate. Significance tests for treatment differences (between Setrusumab doses) will be based on least-squares means (LSMeans).

ANCOVA analyses dealing with nested observations within a patient (e.g., vertebral assessments) will consider this relationship in the modelling by specifying patient as a random factor.

If the input data is log-transformed then LSMean and LSMeans differences between treatment groups will be back-transformed to their original scale for descriptive purposes. After subtracting the geometric mean of the log baseline values, the back-transformed LSMeans will correspond to the percentage change from baseline, while the back-transformed LSMeans differences will correspond to the ratio of percentage changes from baseline.

Time to event variables (e.g., time to first fracture) will be analysed using Kaplan-Meier methods, and quartiles for the median time to event will be presented together with their 95% confidence intervals.

Count variables (e.g number of new fractures) will be analysed using Poisson regression. Analyses will include treatment and randomisation as fixed effects and the logarithm of the duration of exposure to study medication will be included as an offset variable in the model. In case over dispersion is a concern, the negative-binomial regression model will be applied instead.

For binary outcomes the proportion of patients with a response will be summarised and compared between treatment groups using Chi squared test.

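### The primary test sets each dose's ANCOVA LSMean against 0 with OI type as a factor, but the SAP does not say how the LSMean is weighted over OI types, and the software default does not match the sizing when the strata are unequal

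*SAP*

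**What the plan says.** SAP 5 (and Protocol 11.1) frames the primary hypothesis as mu_T ≤ 0 against mu_T > 0, where mu_T "denotes the change from baseline for each dose of Setrusumab". It states that "a sample size of 25 patients per group yields approximately 80% power for a one-sided test with significance level 0.025". That figure is for a t-test of log-transformed values. The planning inputs are a mean change, an SD at each timepoint and a correlation, all blacked out. No stratum enters the calculation.

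The analysis is a different construction. SAP 8.5.2.1 compares LSMeans with zero: those "for each treatment group will be tested against the null hypothesis of 0 using a t-test, in an a priori hierarchical approach", with the highest dose first. It adds that "The type I error rate will be 5% two-sided". Differences between doses are exploratory. The model is in SAP 8.5.1: "Analyses will include the fixed, categorical effects of treatment and randomisation stratum as well as the associated baseline value as a covariate". Protocol 11.3.1 agrees, "using baseline values as a covariate and treatment group and stratum as a factor".

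Randomisation is stratified into Type I and Type III/IV (SAP 3.2.1). Neither document gives an expected split, a quota or a cap. SAP 8.1 names SAS 9.4 or higher and ADDPLAN DF, with no LSMean weighting option.

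**The concern.** An LSMean in a model with a stratum factor is a weighted average over the strata, and the weights are a choice. The usual SAS default weights the factor levels equally, whatever their size. In most trials this does not matter, because in an additive model the weights cancel from differences between arms. Here the confirmatory test is an absolute LSMean against zero, so they remain.

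With equal weights, the test addresses half the Type I change plus half the Type III/IV change. The sizing t-test addresses the average change over the patients in the arm. The two coincide only if the strata are equal in size or respond equally. Even with equal response, up-weighting a small stratum costs precision. The hierarchy starts at the highest dose, so a first step lost this way also blocks the lower doses.

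**Working it through.** **Inputs.** From SAP 5: n = 25 per group, about 80% power, one-sided 0.025. From SAP 6.1: the FAS holds the three blinded arms, so N = 75 if complete. From SAP 8.5.1: three arm terms, one stratum term and one baseline slope, so residual df = 75 − 5 = 70. Assumed: p, the Type I share, the same in every arm; and D, the Type I minus Type III/IV mean change in within-stratum SDs, the same in every arm.

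**The plan's own figure.** Effect, SD and correlation are blacked out, so the 80% cannot be reproduced from its inputs. I back-solve it. For a one-sample t-test with 24 df and critical value 2.064, 80% power needs a mean change of 0.584 SD (noncentrality 0.584 × √25 = 2.92).

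**What the LSMean estimates.** With weight w on Type I:

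- Expected value = mu_T + (w − p)·D
- Variance = σ²·[1/n + (w − p)²/(N·p·(1 − p))]

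Observed margins set w = p. The estimate is then mu_T with variance σ²/n, and power with 70 df (critical value 1.994) is 82.1% at any split. The default sets w = 0.5. With n = 25 and N = 75, the variance is then inflated by 1 + (p − 0.5)²/(3·p·(1 − p)).

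**Equal response in both strata (D = 0).**

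| Split | Variance factor | Noncentrality | Power, equal weights | Power, observed margins |
|---|---|---|---|---|
| 50:50 | 1.000 | 2.920 | 82.1% | 82.1% |
| 60:40 | 1.014 | 2.900 | 81.6% | 82.1% |
| 70:30 | 1.063 | 2.832 | 79.7% | 82.1% |
| 80:20 | 1.188 | 2.680 | 75.3% | 82.1% |
| 90:10 | 1.593 | 2.314 | 62.6% | 82.1% |

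Example at 80:20: 1 + 0.09/(3 × 0.16) = 1.1875, and 2.92/√1.1875 = 2.680. A simulation of the full ANCOVA (10,000 runs) at 80:20 gave 74.3% with equal weights and 81.4% with observed margins.

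**Unequal response.** At 80:20 the tested quantity moves by (0.5 − 0.8)·D. I keep mu_T at 0.584 total SDs, which is 0.584 × √(1 + 0.16 × 0.25) = 0.596 within-stratum SDs for D = ±0.5.

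- D = +0.5 (Type I responds more): target 0.596 − 0.150 = 0.446, power 52%.
- D = −0.5 (Type III/IV responds more): target 0.596 + 0.150 = 0.746, power 92%.
- Observed margins: 84% in both cases.

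**Error rate.** If neither stratum changes, both weightings test a true null and the one-sided error is 2.5% at every split. It shifts only when mu_T = 0 arises from opposite changes in the two strata. At 80:20 the equal-weight test then rejects 10.0% of the time for D = −0.5 and 0.4% for D = +0.5.

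**Baseline related to OI type.** The table treats baseline as unrelated to stratum. If they correlate at r, the second variance term is divided by (1 − r²). For r = 0.4 and 0.6 (assumed), equal-weight power is 74.0% and 71.7% at 80:20, and 59.7% and 54.6% at 90:10.

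**The case against.** The strongest reply is that no contradiction is shown. SAP 5 does not say whether mu_T averages over patients or over strata, and SAP 8.5.1 does not say equal weights. Equal weighting is inferred from software, and an equal-stratum mean is a legitimate target in a trial stratified by OI type. All of this stands. A reader might infer that the plan tests something other than its own null. The text supports only that the weighting is unspecified, that the default is equal, and that the sizing points to a patient average.

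Other parts of the reply also stand:

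- **Size.** The pooled 70 df offset the loss, so against the stated 80% nothing material is lost up to about 70:30. SAP 5 also reports a Month 6 correlation well above the planning value. If that holds at Month 12, the standardised effect for the planned change exceeds 0.584. A 6% larger effect restores 80% at 80:20 under equal response.
- **Severe power loss.** A reader might assume no Type III/IV response at all. At 80:20 the Type I change is then 0.584/0.8 = 0.73, the equal-weight target is 0.365 and power is about 37%. That requires the same gap in all three arms, while Protocol 4.3 expects at least one dose to be sub-therapeutic. If the gap runs 1 : 0.5 : 0 from 20 to 2 mg/kg, the pooled gap is 0.365, the target is 0.584 − 0.3 × 0.365 = 0.474 and power is about 57%. The documents support neither scenario in particular.
- **Error inflation.** A reader might infer a general type I error problem. It arises only if one OI type loses density while the other gains, and nothing in the documents suggests that.
- **Reach.** Many secondary analyses reuse this model, but SAP 8.1.4 and 8.5.1.1 assess them by pairwise comparison, where the weights cancel. MCPMod contrast tests are also between doses.

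SAP 8.5.2.1 already describes change by treatment group and OI type, so divergence between strata would be visible, although not tested. None of this supplies the missing weights for the confirmatory test.

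**Conclusion.** The point holds as an unspecified weighting with a measurable cost under the default. Run as written in SAS, with no option added, the primary test averages Type I and Type III/IV equally, while 25 per group was sized on the patient-average change. With equal response and 0.584 SD, power is about 80% at 70:30, 75% at 80:20 and 63% at 90:10, against 82% with observed margins. With unequal response the tested quantity shifts, and power may go either way.

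These figures rest on a back-solved effect, an assumed split, strata balanced across arms and a complete FAS of 75. Since the split and any response gap are not in the documents, the actual loss in this trial cannot be stated. It may be negligible. Only tests of an LSMean against 0 are affected.

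**What to change.** Before unblinding:

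1. In SAP 5, state that mu_T is the average change over the patients in the arm.
2. In SAP 8.5.1 and 8.5.2.1, state that LSMeans tested against 0 use the observed stratum margins of the analysis set (the OM option in SAS), with baseline at its overall mean.
3. Show equal-weight LSMeans as a sensitivity analysis.

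The cost is a sentence in each place and one option in the code. LSMean differences between doses do not change in this additive model. The small downside is that the reported mean reflects the enrolled OI-type mix. If the sponsor prefers the equal-stratum mean as its target, SAP 5 should say so and the power statement should be redone for the expected split. Fixing the choice now also prevents it from being made after results are seen.

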The HRpQCT results will be log transformed and an ANCOVA model will be used to calculate Least Square Means (LSMeans) for the change from baseline, using baseline values as a covariate and treatment group and stratum as a factor. LSMeans for each treatment group will be calculated and tested against the null hypothesis of 0 in an a priori hierarchical approach, starting with the highest dose. Differences between LSMeans will also be displayed but will be analysed in an exploratory fashion only. The type I error rate will be 5% two-sided. P-values above 5% but below 10% (two-sided) will be considered as indicative for a trend.

The LSMeans will further be analysed using the MCPMod methodology, using the following candidate models:

- EMax (ED₅₀ of 1.5 mg)
- Exponential ($\delta = 2$)
- Sigmoid EMax model with parameters ED50 = 10 mg and h = 2.4

Parameter estimates and predicted values for each dose will be calculated for all models. These analyses will be done primarily on the trabecular vBMD (radius). It will be repeated for the bone strength on FEA for supportive evidence.

LSMeans and LSMean differences between treatment groups will be back-transformed to their original scale for descriptive purposes. After subtracting the geometric mean of the log baseline values, the back-transformed LSMeans will correspond to the percentage change from baseline,

while the back-transformed LSMeans differences will correspond to the ratio of percentage changes from baseline.

The remaining efficacy variables will be analysed according to their scale using general methods as described above.

Exploratory Analyses

Exploratory endpoint variables will be analysed according to their scale using general methods as described above.

Safety Analyses

Variables will be analysed according to their scale using general methods as described above, and results will be presented overall and by treatment group.

Follow-Up Period Analyses

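### The back-transformation rule subtracts baseline from LSMeans that are already log changes, and labels a ratio of post/baseline ratios as a ratio of percentage changes

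*SAP*

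**What the plan says.** Protocol 11.3.1 and the Synopsis (Efficacy Analysis) log-transform the radial trabecular vBMD and state that an "ANCOVA model will be used to calculate Least Square Means (LSMeans) for the change from baseline, using baseline values as a covariate". SAP 8.5.2.1 specifies the same analysis and adds: "The change from baseline LSMMeans for each treatment group will be tested against the null hypothesis of 0 using a t-test".

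Each of these sections then gives a back-transformation rule. In SAP 8.5.2.1 it is "After subtracting the geometric mean of the log baseline values, the back transformed LSMMeans will correspond to the percentage change from baseline". Both Protocol sections have the same sentence, and SAP 8.5.1 repeats it as a general rule for log-transformed input, without itself defining the LSMeans as changes.

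For contrasts between doses, SAP 8.5.2.1 says that "the back-transformed LSMMeans differences will correspond to the ratio of percentage changes from baseline". SAP 8.5.1 and both Protocol sections say the same.

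All four places present the back-transformation as descriptive. SAP section 9 records no change from the Protocol.

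**The concern.** There are two separate faults.

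1. **Baseline is removed twice.** If the LSMean is a log-scale change, as the test against 0 requires, there is no baseline left to subtract. The subtraction belongs to a different model, one with the log post-baseline value as response. Even there, the quantity to subtract is the arithmetic mean of the log baselines (the log of the geometric mean baseline), not a geometric mean of logs.
2. **The labels are wrong.** exp() of a log change is a ratio to baseline. It becomes a percentage change only after subtracting 1 and multiplying by 100. The exponentiated contrast is therefore a ratio of ratios, not a ratio of percentage changes.

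What is at stake is the adjusted effect sizes and dose contrasts that readers will take from the report. The first fault would give absurd numbers and be noticed, but the repair would then be improvised and undocumented. The second gives plausible numbers and could pass unnoticed. It misleads most when a comparator's change is near zero or negative, which is possible here because Protocol 4.3 expects at least one dose to be sub-therapeutic. It also misleads for markers that fall. SAP 8.5.3.7 sends log-transformed biomarkers through the same analysis, and Protocol 4.2 reports earlier decreases in resorption markers.

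**Working it through.** The documents give no figure for this rule, so there is nothing to reproduce. The baseline, SD and effect size in the sample-size sections are redacted. Every baseline, SD and percentage change below is an assumption.

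**Correct algebra.** Let the response be log(post) − log(baseline).

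- Adjusted percentage change = 100 × (exp(LSMean) − 1).
- For two arms with changes a and b, exp(LSMean difference) = (1+a)/(1+b).

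**Label on the contrast** (needs no baseline or SD):

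| Changes a vs b | exp(difference) = (1+a)/(1+b) | Ratio of percentage changes a/b |
|---|---|---|
| +8% vs +2% | 1.08/1.02 = 1.059 | 4.0 |
| +5% vs +0.5% | 1.05/1.005 = 1.045 | 10 |
| +5% vs −1% | 1.05/0.99 = 1.061 | −5 |
| +5% vs 0% | 1.05/1.00 = 1.05 | undefined |
| −20% vs −10% | 0.80/0.90 = 0.889 | 2.0 |

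In the last row the larger fall gives a value below 1. Someone trusting the label would read that as the smaller effect.

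**Literal subtraction from a log change.** A true +5% has LSMean ln(1.05) = 0.0488, and exp(0.0488) − 1 = 5.0%. Subtracting ln(G) first, where G is the geometric mean baseline, gives 1.05/G:

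- G = 50: 1.05/50 = 0.0210
- G = 100: 1.05/100 = 0.0105
- G = 200: 1.05/200 = 0.0053

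Read as changes, these are falls of about 98% to 99%.

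**Alternative reading: LSMeans of log post-values.** A subtraction is then needed, but of the arithmetic mean of the logs. Using the geometric mean of the logs instead inflates the result by exp(AM − GM), where AM and GM are the arithmetic and geometric means of the log baselines (taken as normal, by numerical integration):

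| G | log SD | AM − GM | True +5% shown as |
|---|---|---|---|
| 200 | 0.2 | 0.0038 | 1.05 × 1.0038 − 1 = 5.4% |
| 100 | 0.3 | 0.0098 | 1.05 × 1.0099 − 1 = 6.0% |
| 50 | 0.5 | 0.0326 | 1.05 × 1.0332 − 1 = 8.5% |

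The geometric mean of the logs does not exist if any log baseline is negative. That would happen for BV/TV expressed as a fraction, which SAP 8.5.3.5 analyses by the same method.

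**Check on simulated data.** One data set had three arms of 25, a stratum factor, a log-baseline covariate, baseline centred at 100 with log SD 0.4, and residual SD 0.05. The two correct routes agreed at 9.07%, 3.99% and 2.78%. They were the log-change LSMean with no subtraction, and the log-post LSMean minus the arithmetic mean log baseline. The literal rule gave about −98.9% in every arm. The difference between the first two arms was 0.0477 on the log scale under either response.

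**The case against.** **Nothing decisive depends on it.** This stands. The tests against 0, the p-values and the MCPMod step use the log-scale LSMeans, and those LSMeans are displayed with standard errors. SAP 8.5.2.1 also plans an unadjusted summary of percentage change by arm. That summary does not correct the adjusted estimates or the contrast labels.

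**The authors may have meant LSMeans of log post-values.** There is some room for this. SAP 8.5.1 does not define the LSMeans as changes, and SAP 8.5.2.1 plans "Line graphs of the LSmean HRpQCT results (+/- SE) and change from baseline in HRpQCT results (+/- SE) will be presented", so both quantities may be produced. But this reading conflicts with the change LSMeans stated in the Synopsis, Protocol 11.3.1 and SAP 8.5.2.1. It would still need the arithmetic mean of the logs, and no section says which reading applies.

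**Percentage change may loosely mean follow-up as a percentage of baseline.** The sentence would then be self-consistent and the fault only one of terminology. But SAP 8.5.2.1 uses percentage change from baseline in its ordinary sense for the raw summary, so one term would carry two meanings within one section.

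**The near-zero comparator is not predicted.** This is fair. Sub-therapeutic in Protocol 4.3 concerns benefit, not the size of the density change. Reading mg as mg/kg, the Protocol's EMax candidate puts 2 mg/kg at 2/(2 + 1.5) = 57% of maximum, while its Sigmoid EMax (ED50 10, h 2.4) puts it at about 2%. The documents allow a near-zero comparator but do not forecast one. Likewise, Protocol 4.2 reports marker falls in earlier studies, not in this trial.

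**Conclusion.** The rule is wrong as written. The Synopsis, Protocol 11.3.1 and SAP 8.5.2.1 subtract baseline from a quantity that is already a change. Those three and SAP 8.5.1 all mislabel the exponentiated difference. The label fault is pure algebra and rests on no assumption about baseline or variability; the percentage pairs only illustrate its size. The size of the subtraction error depends on assumed baselines and SDs, but the conclusion that the sentence cannot be programmed as it stands does not, unless the geometric mean baseline were close to 1. Severity is minor, because the harm is limited to descriptive adjusted effect sizes and contrast labels.

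**What to change.** In the Protocol Synopsis, Protocol 11.3.1, SAP 8.5.1 and SAP 8.5.2.1, delete the baseline subtraction and the description of the back-transformed difference. Replace them with:

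> For log-transformed data the ANCOVA response is log(post-baseline value) − log(baseline value). The adjusted percentage change is 100 × (exp(LSMean) − 1), with confidence limits transformed the same way. exp(LSMean difference) is the ratio of adjusted geometric mean post/baseline ratios.

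Align the wording of SAP 8.5.3.1 (tibia), which already refers to 8.5.2.1. If the Protocol is not amended, record the correction in SAP section 9.

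The cost is text in four places plus any matching table labels. The table templates are in a separate document, so that part is presumed. No data, test or sample size changes.

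The scale of the baseline covariate is a separate point. SAP 8.5.1 says only "as well as the associated baseline value as a covariate", and the correction above does not depend on it. One clarifying sentence before unblinding would still be useful, since log-change and log-post models agree exactly only with a log-baseline covariate.
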